### **10.4.3 Analysis of the Secondary Endpoint(s)**

All secondary efficacy analyses will be performed based on the FAS.

#### **Overall Response Rate (ORR)**

Overall response rate is defined as the proportion enrolled subjects who achieve a best response of partial response (PR) or better using the Modified criteria of the International Myeloma Working Group (IMWG) ([see Appendix 4](#)) as their best overall response.

The response rate, along with its exact two-sided 95% CI, will be computed.

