## 7. Study procedures and Schedule

### 7.1 Study Procedures/Evaluations

#### 7.1.1 Efficacy Assessments

The primary endpoint of this study is Progression Free Survival (PFS). Secondary efficacy endpoints are Overall Survival (OS), Overall Response Rate (ORR), Renal Response Rate (RRR), duration of response and time to next therapy.

Response or disease progression will be assessed by the Investigator based on the analysis of serum and urine protein electrophoresis (sPEP and uPEP), serum and urine immunofixation (sIFE, uIFE), serum free light chain protein (sFLC), imaging and bone marrow assessments as per IMWG guidelines (see [Appendix 4](#)). If the patient does not have documented disease progression as defined in [Appendix 4](#) at the time of study drug discontinuation, then tumor assessments must continue to be performed according to the same schedule shown in [Table 7.2](#) until disease progression even if a subsequent anti-myeloma treatment is started prior to disease progression.

Assessment of renal response will be conducted in accordance with the International Myeloma Working Group (IMWG) response criteria, based on eGFR calculated by the CKD-EPI formula.

All study assessments and laboratory tests will be performed according to standard clinical practice and as clinically indicated.

Assessments performed at external laboratories may be accepted as per institutional practice.

Disease assessments are shown in Table 7.1.

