**Table 7.1 – Disease assessments**

M-protein by electrophoresis Serum (sPEP), Urine (uPEP)	Screening and baseline Day one of each cycle End of treatment Post-treatment follow-up every 4 weeks As needed to confirm disease progression
M-protein by immunofixation Serum (sIFE), Urine (uIFE)	Screening and baseline End of treatment Post-treatment follow-up every 4 weeks As needed to confirm CR (when PEP is 0 or non-quantifiable)
Serum free light chain sFLC	Screening and baseline Day one of each cycle (for patients that have no measurable serum or urine M-protein) As needed to confirm sCR End of treatment Post-treatment follow-up every 4 weeks As needed to confirm disease progression
Clinical assessment of soft tissue plasmacytoma (STP)	Screening and baseline Day one of each cycle End of treatment Post-treatment follow-up every 4 weeks As needed to confirm disease progression
CT/MRI assessment of STP	If present or suspected, at screening and as clinically indicated.
Plasma cell count in bone marrow	At screening and during the study as clinically indicated to substantiate CR and PD for patients with non-measurable disease by M protein in serum and urine as well as by FLC.
Skeletal survey by X-ray and/or CT/MRI	At screening and as clinically indicated, CT/MRI in case of newly symptomatic areas with no X-ray finding.
Serum Creatinine (for patients not on dialysis)	Screening and baseline Weekly in the first two cycles then every two weeks for cycles 3-6 and then on day one of each cycle End of treatment Post-treatment follow-up every 4 weeks
Corrected calcium	Screening and baseline Day one of each cycle End of treatment Post-treatment follow-up every 4 weeks As needed to confirm disease progression
MRD by means of EuroFlow next generation cytometry	If required for confirmation of sCR, upon confirmed CR/sCR and thereafter every 6 months as long as CR/sCR is maintained.

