## 7.2.3 Follow-up Period

### Post-treatment follow-up

Patients who discontinue treatment for reasons other than documented disease progression, death, lost to follow-up, or withdrawal of consent should continue to be followed for response assessments every 4 weeks as in [Table 7.2](#). The reason for completion/discontinuation should be recorded on the eCRF.

If a patient starts new anti-neoplastic therapy prior to disease progression, every attempt should be made to perform tumor evaluations until documented disease progression. In addition, all new anti-neoplastic therapy administered starting from the last dose of the study treatment until death, lost to follow-up, or withdrawal of consent will be recorded in the eCRF.

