### **Progression Free Survival (PFS)**

Progression free survival is defined as the time, in months, from treatment initiation (Cycle 1 , day 1) to the date of the first documented disease progression or death due to any cause, whichever comes first. Clinical deterioration will not be considered progression. For subjects who neither progress nor die, the survival time will be censored at the date of their last disease assessment. For subjects who start a new anti-tumor treatment, survival time will be censored at the date of the start of the new treatment.

The PFS function will be estimated using the Kaplan-Meier product-limit method. Median and two-sided confidence intervals (CI) for median PFS will be computed by and Kaplan-Meier plots of PFS will be presented.

Absolute frequencies and proportions of patients with disease progression or all-cause death will also be provided.

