#### **Renal Response Rate (RRR)**

Renal Response Rate is defined as the proportion enrolled subjects who achieve a best response of renal partial response (PRRenal) or better using the criteria of the International Myeloma Working Group (IMWG) ([see Appendix 5](#)).

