#### **Duration of Response (DoR)**

Duration of response will be restricted to the subjects that achieve a best objective response of PR or better. It is measured from the time, in months, that the criteria for objective response are first met until the date of a progression event (according to the primary definition of PFS). A subject with objective response who does not have a progression event will be censored at the same time they were censored under the primary definition of PFS.

The DoR function will be estimated using the Kaplan-Meier product-limit method. Median and two-sided confidence intervals for median duration of response will be computed and Kaplan-Meier plots of DoR will be presented.

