6.6.1.4 Secondary Endpoint Analysis

All secondary efficacy analyses will be performed based on the FAS.

Overall Response Rate (ORR)

ORR is defined as the proportion enrolled subjects who achieve a best response of partial response (PR) or better using the Modified criteria of the IMWG (

Rajan, A. M., and S. V. Rajkumar. "Interpretation of cytogenetic results in multiple myeloma for clinical practice." *Blood cancer journal* 5.10 (2015): e365.

Health Data Specialists	
DARE (EAE-2017/MM02)- Statistical Analysis Plan	Version: 1.0 EN
Author: GC, Reviewer: MS, Quality Assurance: GK	Date: 02-02-2018

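### ORR and RRR take the best response with no end date, so a response first reached on a later anti-myeloma therapy, started before progression, can be credited to daratumumab-dexamethasone

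*Protocol*

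**What the plan says.** **Response definitions.** Protocol 10.4.3: "Overall response rate is defined as the proportion enrolled subjects who achieve a best response of partial response (PR) or better". For the kidney: "Renal Response Rate is defined as the proportion enrolled subjects who achieve a best response of renal partial response (PRRenal) or better". SAP 6.6.1.4 has the same ORR rule, "ORR is defined as the proportion enrolled subjects who achieve a best response of partial response (PR) or better", and an equivalent one for RRR. None of these sets an assessment window or says what happens once another therapy begins.

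**Assessments after study drug stops.** Protocol 7.1.1 keeps tumor assessments on schedule "until disease progression even if a subsequent anti-myeloma treatment is started prior to disease progression". Section 7.2.3 says that for patients who start new therapy before progression "every attempt should be made to perform tumor evaluations until documented disease progression". Table 7.2 marks investigator response assessment in the four-weekly post-treatment follow-up, and marks other anti-neoplastic therapies there too. For creatinine in patients not on dialysis, Table 7.1 reads "and then on day one of each cycle End of treatment Post-treatment follow-up every 4 weeks".

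**Time-to-event endpoints.** PFS has a cut-off in Protocol 10.4.2 (SAP 6.6.1.3 matches): "For subjects who start a new anti-tumor treatment, survival time will be censored at the date of the start of the new treatment". DoR starts when the response criteria are first satisfied, and a responder without a progression event "will be censored at the same time they were censored under the primary definition of PFS".

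**The concern.** PFS and DoR stop at the start of the next therapy; ORR and RRR do not. Read literally, the response rates can include an effect of a different drug. In a single-arm trial no control group shows or offsets this, and the error runs one way: an added response can only raise the rate. The exact confidence interval planned for ORR does not cover it.

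The SAP gives a programmer little reason to assume an on-treatment window. One of its subgroups is defined by any eGFR above 30 across the entire observation period (SAP 6.5.4). It also plans to compare PFS, OS and ORR between renal responders and non-responders (SAP 6.6.1), so a misattributed renal response would carry into those comparisons.

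**Working it through.** **1. Is a cut-off given elsewhere?** Protocol 10.4.3, SAP 6.6.1.4 and the response appendices contain none. Footnote 3 of Protocol Appendix 4 mentions new therapy, but only for classifying relapse or progression, not for best response.

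**2. Who is exposed?** All four conditions must hold:
- the patient stops study drug without documented progression;
- another anti-myeloma therapy starts before progression;
- there was no qualifying response beforehand;
- the first qualifying response is recorded under the new therapy.

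The protocol allows for this path. Section 5.3.1 lists reasons other than progression for stopping, section 6.1.5 adds toxicity holds beyond 28 days, and sections 7.1.1, 7.2.3 and 10.4.2 all provide for a new therapy before progression.

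**3. What happens to DoR?** Let t_new be the start of the new therapy and t_resp the date of first response. For an exposed patient t_resp > t_new. PFS is censored at t_new and DoR takes the same censoring date, so

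DoR = t_new − t_resp < 0.

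Neither document says how to handle such a value.

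**4. Size per patient.** The plan has no target, hypothesis or power for ORR or RRR, so there is no figure of its own to reproduce on this point. The denominator is the planned 38 (Protocol 10.5: 34/(1 − 0.10) = 37.8, rounded up). Each misattributed response adds 1/38 = 2.6 percentage points.

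**5. Illustration for ORR.** The Phase 2 monotherapy study quoted in Protocol 1.2 had an ORR of 29.2%; 0.292 × 38 = 11.1, so take 11 true responders. Exact two-sided 95% intervals:

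| Responders counted | ORR | 95% CI |
|---|---|---|
| 11 (none misattributed) | 28.9% | 15.4 to 45.9 |
| 12 (1 extra) | 31.6% | 17.5 to 48.7 |
| 13 (2 extra) | 34.2% | 19.6 to 51.4 |
| 15 (4 extra) | 39.5% | 24.0 to 56.6 |

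**6. Range under stated assumptions.** The documents give neither the share switching before progression (q) nor the response rate on the next therapy (r). Assume q = 5% to 20% and r = 20% to 60%.
- If no switcher had responded earlier, the inflation is q × r: from 0.05 × 0.20 = 1.0 point (38 × 0.01 = 0.38 patients) to 0.20 × 0.60 = 12.0 points (38 × 0.12 = 4.56 patients).
- If 29.2% of switchers had already responded, it is q × (1 − 0.292) × r: 0.7 to 8.5 points.

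With a cut-off at the start of the next therapy it is zero.

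**7. Is the renal data there?** Table 7.1 schedules creatinine every four weeks after treatment for patients not on dialysis. The eGFR row of Table 7.2, as it reads in the available text, has no entry after the end-of-treatment visit. The two tables do not agree.

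**The case against.** The strongest objection is that the protocol largely closes this path. Under the sponsor-confirmation heading in section 7.1.1, the next therapy should begin only once the sponsor has confirmed progression. After progression, section 7.2.3 collects only survival and subsequent therapy. Section 7.2.2 asks for the end-of-treatment visit before the next therapy where possible. A patient who switches at progression therefore has no scheduled response assessment under the new drug. This stands, and it limits the point to switches before progression. It does not remove the point, because the protocol expects such switches and keeps assessing those patients.

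A reader might infer more in three ways, none of which the documents support:
- **That responses to other drugs will be counted.** The text shows only that they can be. It gives no number of patients on this path.
- **That RRR is the endpoint most exposed.** The rules for continuing after a new therapy refer to tumor assessments, not renal function, and the schedules conflict on post-treatment renal data. Under Appendix 5, a move from a baseline eGFR of 15-29 to 30-59 is only a minor response and does not count. Protocol 1.3 also says that renal recovery is less frequent in relapsed/refractory disease.
- **That the 10% drop-out allowance predicts about four switchers.** It inflates 34 to 38 and says nothing about switching. Patients lost to follow-up or withdrawing consent leave the four-weekly assessments, so they cannot produce such responses.

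It is also fair that these are secondary endpoints without a formal test, that one or two extra responders are small beside the width of the interval, and that a negative DoR would be noticed in programming. Tying DoR to PFS censoring suggests the intended window, but the response definitions do not state it.

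**Conclusion.** The point holds as a gap in the definitions that can bias ORR upward and is inconsistent with the plan's own DoR rule. The same gap exists for RRR, but whether it matters there depends on which schedule governs post-treatment creatinine.

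The only size that follows from the documents is 2.6 percentage points per affected patient, at 38 patients. The wider range above rests on assumed switching and response rates and is not a forecast. PFS, the primary endpoint, is unaffected. The correction is worth making because the bias has one direction, the trial has no comparator, and the needed rule is short.

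**What to change.** In Protocol 10.4.3 and SAP 6.6.1.4, state that best myeloma response and best renal response use only assessments from Cycle 1 Day 1 up to the earlier of documented progression and the start of any subsequent anti-myeloma therapy. Keep all FAS patients in the denominator, so that those without a qualifying response in the window count as non-responders. Apply the same window to DoR, which rules out negative durations. The all-assessments version can be reported as a sensitivity analysis.

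Separately, reconcile the creatinine row of Table 7.1 with the eGFR row of Table 7.2 for the post-treatment period.

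The cost is about one sentence per document plus the schedule correction. No new data are needed: new therapies are already recorded in the eCRF (Protocol 7.2.3) and progression dates are required for PFS. The downside is that ORR and RRR may come out slightly lower.

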#### **Renal Response Rate (RRR)**

Renal Response Rate is defined as the proportion enrolled subjects who achieve a best response of renal partial response (PRRenal) or better using the criteria of the International Myeloma Working Group (IMWG) ([see Appendix 5](#)).

#### **Duration of Response (DoR)**

Duration of response will be restricted to the subjects that achieve a best objective response of PR or better. It is measured from the time, in months, that the criteria for objective response are first met until the date of a progression event (according to the primary definition of PFS). A subject with objective response who does not have a progression event will be censored at the same time they were censored under the primary definition of PFS.

The DoR function will be estimated using the Kaplan-Meier product-limit method. Median and two-sided confidence intervals for median duration of response will be computed and Kaplan-Meier plots of DoR will be presented.

#### **Time to Next Therapy (TNT)**

Time to next therapy will be defined as the time, in months, from Cycle 1 Day 1 to the date to next anti-neoplastic therapy or death from any cause, whichever comes first. For subjects who neither start a new

anti-neoplastic therapy nor die, survival time will be censored at the date of their last available follow-up assessment.

Time to next therapy will be calculated using a log-rank test procedure. The TNT function will be estimated using the Kaplan-Meier product-limit method. Median and two-sided confidence intervals for median TNT will be computed. Kaplan-Meier plots of TNT will be presented.

### **Overall Survival (OS)**

Overall survival is defined as the time, in months, from the first dose of therapy to the date of death from any cause. If a patient is not known to have died, survival time will be censored at the date of last contact (“last known date alive”).

Overall survival will be estimated using the Kaplan-Meier product-limit method. Median and corresponding two-sided 95% confidence intervals will be computed. Kaplan-Meier plots of OS will be presented.

### **10.4.4 Safety Analyses**

Safety analyses will be conducted on the Safety Set and will be reported.

#### **Adverse events**

AEs will be assessed according to the Common Terminology Criteria for AEs (CTCAE version 4.03).

The incidence of AEs will be tabulated by MedDRA System Organ Class and Preferred Term. The incidence of AEs will also be summarized by system organ class, preferred term and severity (based on CTCAE grades).

The same analysis will be repeated for SAEs regardless of drug relationship, for drug related SAEs, AEs with CTCAE grade 3 or 4 and for drug related AEs. AEs for which relationship to study drug is not specified will be considered treatment-related.

Deaths reportable as SAEs will be listed by patient and tabulated by type of AE.

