#### **4.1.2 Secondary Endpoints**

- Overall response rate
- Renal Response rate
- Duration of response
- Time to next therapy
- Overall survival
- Safety (adverse events)

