### 7.1.2.1 Adverse events

Monitoring for adverse events will take place continuously throughout the study, starting from informed consent until 30 days after last study treatment. See [Section 8](#) for details.

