**Table 7.2 – Schedule of Events**

Day of Cycle (28-days)	Screening ^	Treatment: visit window during the treatment period is +/- 3 days												End of treatment EOT 	Survival follow-up Every 12 weeks	
		Cycles 1 and 2				Cycles 3-6				Cycles 7 and beyond						
		-21 to 1	1 BL	8	15	22	1	8	15	22	1	8	15	22		
Demographic/baseline Assessments																
Informed consent	X															
Demography	X															
Inc./Exc. criteria	X															
Medical history	X															
MM diagnosis/history	X															
International Staging System (ISS)	X															
Cytogenetics (FISH) at study entry	X															
Safety Assessments																
Physical examination	X	X					X				X			X		
Vital signs	X	X	X	X	X	X		X		X				X	X	
Weight	X	X	X	X	X	X		X		X				X	X	
Performance status (ECOG)	X	X				X				X				X		
Adverse Events	Continuously from ICF until 30 days after last study treatment												Treatment related SAEs			
Concomitant medication, transfusions	X	X	X	X	X	X	X	X	X	X	X	X	X	X		
Cardiac imaging: ECHO or MUGA 	X	As clinically indicated														
FEV1***	X															
ECG	X	As clinically indicated														
Lab Assessments*																
Blood type assessment and indirect antiglobulin results 	X															
Hematology	X	X	X	X	X	X		X		X				X		
Clinical chemistry	X	X	X	X	X	X		X		X				X		
eGFR	X	X	X	X	X	X		X		X				X		
Pregnancy test 	X	X														

^	Screening	Treatment: visit window during the treatment period is +/- 3 days												End of treatment EOT 	Post treatment FU Every 4 weeks 	Survival follow-up Every 12 weeks													
		Cycles 1 and 2				Cycles 3-6				Cycles 7 and beyond																			
		-21 to 1	1 BL	8	15	22	1	8	15	22	1	8	15	22															
Day of Cycle (28-days)																													
Serum $\beta$ 2-microglobulin, LDH		X																											
Hepatitis B serology 		X																											
HBV-DNA PCR testing 		X	Every 12 weeks (window $\pm$ 7 days)												X	Every 12 weeks for up to 6 months after the last dose of study treatment													
Efficacy Assessments																													
Efficacy / Disease Assessment required to confirm response or disease progression should be performed as soon as possible after response or disease progression is suspected – see Section 7.1 for details)																													

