## **8.3 Time Period and Frequency for Event Assessment and Follow-Up**

The occurrence of an AE or SAE may come to the attention of study personnel during study visits and interviews of a study participant presenting for medical care, or upon review by a study monitor. All AEs including local and systemic reactions not meeting the criteria for SAEs will be captured on the eCRF. Information to be collected includes event description, time of onset, clinician's assessment of severity, relationship to study product (assessed only by those with the training and authority to make a diagnosis), and time of resolution/stabilization of the event. All AEs occurring while on study must be documented appropriately regardless of relationship. All AEs will be followed to adequate resolution.

Any medical condition that is present at the time that the participant signs the ICF will be considered as baseline condition and not reported as an AE. However, if the study participant's condition deteriorates in severity and frequency at any time during the study, it will be recorded as an AE.

Changes in the severity of an AE will be documented to allow an assessment of the duration of the event at each level of severity to be performed. AEs characterized as intermittent require documentation of onset and duration of each episode.

The Investigator will record all reportable events with start dates occurring any time after informed consent is obtained until 30 days (both AEs and SAEs) after the last day of study treatment. At each study visit, the investigator will inquire about the occurrence of AE/SAEs since the last visit. Events will be followed for outcome information until resolution or stabilization.

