### **Concomitant treatments**

Concomitant medications or procedures and significant non-drug therapies taken concurrently with the study treatment will be listed and summarized by WHO Anatomical Therapeutic Chemical (ATC) Class, Preferred Term. These summaries will include medications starting on or after the start of study treatment (defined as cycle 1 day 1) or medications starting prior to the start of study treatment and continuing after the start of study treatment. Any prior medication or significant non-drug therapy starting and ending prior to the start of study treatment will be listed.

For the analyses of transfusions, only transfusions received after start of study treatment and up to 30 days after last dose will be considered. The number of patients with transfusions and number of transfusions per patient will be analyzed.

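### Adverse events are collected from consent but tabulated with no onset window, so pre-dose events in dosed patients enter the all-causality safety tables

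*Protocol*

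**What the plan says.** **Collection.** Protocol 7.1.2.1 has AE monitoring run "starting from informed consent until 30 days after last study treatment". The schedule of events (Table 7.2) agrees: "Continuously from ICF until 30 days after last study treatment". Section 8.3 sets the recording period by onset: "start dates occurring any time after informed consent is obtained until 30 days (both AEs and SAEs) after the last day of study treatment". Section 7.1.2.4 sends significant findings that are new or worse since consent to the AE page. Screening may occupy the 21 days before Cycle 1 Day 1 (7.2.1).

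**Tabulation.** Protocol 10.4.4 gives the basic table: "The incidence of AEs will be tabulated by MedDRA System Organ Class and Preferred Term". SAP 6.6.1.5 has the same sentence. Both go on to tables by grade, and repeat the analysis for SAEs of any causality, related SAEs, grade 3 or 4 AEs and related AEs. No onset date limits any of these tables. The Safety Set (10.3; SAP 6.5.3) requires at least one dose, so it selects patients and not events.

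**Missing causality.** Both documents add the rule: "AEs for which relationship to study drug is not specified will be considered treatment-related".

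**Windows set elsewhere.** For transfusions (10.4.6; SAP 6.6.1.6), "only transfusions received after start of study treatment and up to 30 days after last dose will be considered". Laboratory grades are summarised as worst post-baseline values, and shift tables use the worst on-treatment value.

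**The concern.** Adverse events are a listed secondary endpoint (4.1.2), and the trial has one arm. A randomised comparison would carry pre-dose events in both arms and they would roughly cancel. Here nothing offsets them, and each one that counts pushes the reported rate upward.

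The population makes such events plausible: relapsed or refractory myeloma with eGFR below 30 or dialysis, in the weeks before a new treatment. An infection or a fall in blood counts during screening, in a patient who is then dosed, would be counted with events that arose on treatment.

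The missing-causality default raises a second, narrower issue. It has no onset condition, so a pre-dose event with a blank relationship field would be reported as drug-related, although it began before any study drug was given.

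**Working it through.** The plan states no figure on this point, so there is none to reproduce. The check has two parts: tracing which events the text admits to each table, and illustrating the possible size.

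**1. Tracing a screening event in a patient who is later dosed**

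| Step | Rule | Result |
|---|---|---|
| Present at consent? | 8.3: a baseline condition, not an AE | Excluded |
| Begins or worsens after consent, before first dose? | 7.1.2.1, 7.1.2.4, 8.3 | Recorded as an AE |
| Patient never dosed? | Safety Set | Excluded |
| Patient dosed? | Safety Set | Patient's events retained |
| All-causality AE, SAE and grade 3-4 tables | 10.4.4, SAP 6.6.1.5: no onset limit | Counted |
| Drug-related tables, causality entered as not related | 8.2.2, 10.4.4 | Not counted |
| Drug-related tables, causality blank | Missing-causality default | Counted |

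The gap therefore covers events that begin or worsen between consent and first dose, in dosed patients. Neither document says outright that these will be tabulated. That follows from collection starting at consent and the absence of any restriction.

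**2. Share of the collection window that is pre-dose**

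Share = screening days / (screening days + treatment days + 30).

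Inputs: 30 days of post-treatment collection (8.3) and 21 days as the screening maximum (7.2.1). The 14-day and 7-day screening periods and the treatment durations are assumptions.

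| Treatment | 21 days' screening | 14 days' screening |
|---|---|---|
| 28 days (one cycle) | 21/79 = 27% | 14/72 = 19% |
| 152 days (about 5 months) | 21/203 = 10% | 14/196 = 7% |
| 365 days | 21/416 = 5% | 14/409 = 3% |

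With 7 to 21 days of screening and 3 to 5.6 months of treatment, the range is 3% to 15%. These are shares of calendar time. They equal shares of events only if the AE rate is constant.

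**3. Effect on patient-level incidence, by assumption**

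Let p be the on-treatment risk and q the pre-dose risk of a given event, taken as independent. Tabulated incidence = 1 - (1 - p)(1 - q), so the increase is q(1 - p).

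- Smallest case: p = 0.50, q = 0.02. Increase = 0.02 × 0.50 = 0.01, or 0.4 of 38 patients.
- Largest case: p = 0.10, q = 0.10. Increase = 0.10 × 0.90 = 0.09, or 3.4 of 38 patients.

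No value of p or q comes from the documents. If the same patients tend to have the event both before and after first dose, the increase is smaller.

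**The case against.** A reader might infer that the plan charges pre-dose events to daratumumab and dexamethasone. The documents do not support that. The AE, SAE and grade 3-4 tables are all-causality, so an entry there attributes nothing to treatment. Only the drug-related tables attribute. Section 8.2.2 requires a causality judgement for every collected AE and offers a category for events independent of the study drug. Section 8.3 lists relationship among the items to be collected, and Section 14.1 provides on-line checks, queries and investigator certification of completeness. Nothing suggests that the field would routinely be blank for screening events.

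The size is also open to challenge. Twenty-one days is the screening maximum, and the 27% figure pairs it with a single cycle. A constant rate does not fit the protocol's own account of the drug. Section 6.1.4 reports infusion reactions in about half of patients, mostly at the first infusion. Section 1.2 cites 48% of patients in one phase 3 trial, with 92% of the reactions at the first infusion. Events therefore cluster after dosing, and the time share probably overstates the pre-dose share of events. If incidence is counted by patient, a pre-dose event that recurs on treatment under the same term adds nothing.

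Finally, no test or numerical threshold rests on these rates. The safety review at 19 patients (10.4.7.1) is an overall evaluation, not a rate rule. The primary endpoint is untouched, and any bias overstates harm rather than hiding it.

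All of this stands as a limit on size and on attribution. It does not supply the missing window. A programmer might add a treatment-emergent flag unprompted, but the plan does not require one, so two programmers following it could produce different tables.

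**Conclusion.** The point holds as a gap in the counting rule, with a modest effect. Followed as written, 10.4.4 and SAP 6.6.1.5 put pre-dose events of dosed patients into the all-causality AE, SAE and grade 3-4 tables, and the error runs in one direction in a trial without a control arm. The transfusion and laboratory analyses show that the authors set a window when they considered it, so this is more than a matter of drafting detail.

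Entry into the drug-related tables is a secondary issue. It needs a blank causality field, or a pre-dose event marked as related, and either should be uncommon.

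The size cannot be derived from the documents. The 3% to 27% range describes calendar time under an assumed constant rate, and the range of 1 to 9 percentage points rests on assumed risks and independence. Neither should be quoted as the expected bias. What is certain is that neither document gives an onset window or a treatment-emergent definition for these tables.

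**What to change.** In protocol 10.4.4 and SAP 6.6.1.5:

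- Define a treatment-emergent event as one that starts or worsens from the first dose of study treatment to 30 days after the last dose. Base all the AE, SAE, grade 3-4 and drug-related incidence tables on it.
- Keep SAEs reported after day 30 as suspected to be related (8.4.2), either in the related-SAE table or in a separate listing, so that the new limit does not drop them.
- List events with onset between consent and first dose separately.
- Apply the missing-causality default only to events with onset on or after the first dose.
- Use the same definition for the data given to the safety review at 19 patients. Protocol 10.4.7.1 leaves the detail of that review to the SAP, and SAP 6.5.5 marks interim analysis as not applicable.

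The cost is a wording change, one flag derived from onset and dosing dates already collected, and one extra listing. Reported AE rates would be slightly lower than under the present text.
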